8.1 Disease Evaluability

- **8.1.1 Measurable Disease:** Bidimensionally measurable lesions with clearly defined margins by MRI scan.
- 8.1.2 Evaluable Disease: Unidimensionally measurable lesions, masses with margins not clearly defined. Patients with only this kind of imaging will not be allowed to enter this study unless they have recently undergone surgery and have histologically proven recurrent disease.
- 8.1.3 Non-Evaluable Disease: Not Applicable.
- 8.1.4 Objective Status, To Be Recorded at Each Evaluation: If there are too many measurable lesions to measure at each evaluation, choose the largest two to be followed before a patient is entered on study. The remaining

lesions will be considered evaluable for the purpose of objective status determination. Unless progression is observed, objective status can only be determined when ALL measurable and evaluable sites and lesions are assessed.

8.2 **Response Criteria**

- 8.2.1 Complete Response (CR): Complete disappearance of all measurable and evaluable disease. No new lesions. No evidence of non-evaluable disease. All measurable, evaluable and non-evaluable lesions and sites must be assessed using the same techniques as baseline. Responders must be on none or only maintenance doses of dexamethasone.
- **8.2.2 Partial Response (PR):** Greater than or equal to 50% decrease under baseline in the sum of products of perpendicular diameters of all measurable lesions. No progression of evaluable disease. No new lesions. All measurable and evaluable lesions and sites must be assessed using the same techniques as baseline. Responders must be on the same or decreasing doses of dexamethasone and have stable or improved neurological exams.
- 8.2.3 Partial Response, Non-Measurable (PRNM): Not applicable.
- **8.2.4** Stable/No Response: Does not qualify for CR, PR, or progression. The designation of Stable/No Response requires a minimum of 8 weeks duration. All measurable and evaluable sites must be assessed using the same techniques as baseline. Responders must be on the same or decreasing doses of dexamethasone and have stable or improved neurological exams.
- **8.2.5 Progression:** 25% increase in the sum of products of all measurable lesions over smallest sum observed (over baseline if no decrease) using the same techniques as baseline, OR clear worsening of any evaluable disease, OR appearance of any new lesion/site, OR failure to return for evaluation due to death or deteriorating condition (unless clearly unrelated to this cancer).
- **8.2.6** Unknown: Progression has not been documented and one or more measurable or evaluable sites have not been assessed.

8.3 Note:

- **8.3.1** For evaluable disease other than types specified in Section 8.1.2, the only objective statuses which apply are CR, stable/no response, progression and unknown.
- **8.3.2** Objective status must stay the same or improve over time until progression (unknown excepted).
- 8.4 Neurological Exam: Although not used for determining response, it is useful to evaluate improvement in the neurologic exam that should coincide with objective measurement of tumor size.

- 1 Normal exam
- 2 Improvement from on-study state (patient better)
- 3 Same as on-study state (patient same).
- **4** Worse than on-study state (patient worse).
- **8.5** **Performance Status:** Patients will be graded according to Karnofsky Performance Status (see Appendix G).
- 8.6 **Progression Free Survival (PFS)**: From date of registration to the date of first observation of progressive disease, non-reversible neurologic progression or permanently increased steroid requirement (applies to stable disease only) or death due to any cause. Progression Free Survival (PFS) in patients enrolled in the surgical arm will be determined from the date of randomization (i.e. after surgery for resection of recurrent tumor), and not from the date of registration in the trial.
- 8.7 **Survival:** From date of registration to date of death due to any cause.
- **8.8** Steroids: Steroid dosage will be carefully monitored and recorded during each course of therapy and steroid dosage changes will be considered before response determinations are made.
- **8.9** Unacceptable toxicity: grade 3 or greater toxicity after 3 dose reductions of temozolomide or 2 dose reduction of any of the other drugs, or after 1 dose reduction if starting dose of vorinostat is 300 mg orally once daily.

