5.2.2. Surgical Arm

Ten patients who require resection for recurrent glioblastoma multiforme will be included in this arm of the study. These patients will receive treatment with vorinostat at a dose of 400 mg once daily for 3 consecutive days prior to surgery. Blood samples for acetylation status of histones and p21 levels in peripheral mononuclear cells will be collected at baseline prior to treatment, and after the first dose of vorinostat. The last dose prior to surgery will be administered the morning of surgery within 6 hours of the tumor removal. Tumor tissue and intraoperative blood samples will be obtained for analysis of drug levels, histone acetylation and p21 levels. Approximately 2 weeks after surgery is performed, each patient will be randomized to one of the three treatment arms of the phase II component (arm 1: vorinostat + cRA; arm 2: TMZ + cRA; arm 3: vorinostat + cRA + TMZ). Patients enrolled in arms 1 and 3 will be evaluated with blood samples before and after treatment with vorinostat in cycles 1 and 2 as described for patients in the non-surgical arm (see 5.2.1, and 7.10). In surgical patients, cycle 1 will be the first cycle of treatment after surgery.

Progression Free Survival (PFS) in patients enrolled in the surgical arm will be determined from the date of randomization into the chemotherapy arms (i.e. after surgery for resection of recurrent tumor), and not from the date of registration in the trial.

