11.2 Phase II component

This is an adaptive randomized phase II trial to compare three treatment arms: a) vorinostat + Isotretinoin, b) Temozolomide + Isotretinoin, and c) vorinostat + Isotretinoin + Temozolomide, in patients with recurrent GBM. The primary outcome is Progression Free Survival (PFS). Patients will be randomized among arms using a Bayesian adaptive algorithm. Technical details of this methodology are given in Appendix H. Patients will be randomized fairly among the three arms at the start of the trial (for the first 30 patients). Thereafter, as the trial progresses and data accrue, the randomization will become unbalanced in favor of the

treatment that, on average, has better results in terms of failure time. Therefore, each successive patient is more likely to receive the treatment with better results, on average. A minimum of 30 and a maximum of 135 patients will be accrued and there will be 6 months follow up after the last patient is accrued. Based on an anticipated accrual rate between 3 and 5 patients per month, the maximum trial accrual period will be between 45 and 27 months.

Patients enrolled in the surgical arm of the phase II component will be randomized to one of the three treatment arms after surgery is performed. In surgical patients, cycle 1 will be the first cycle of treatment after surgery. PFS in these patients will be determined from the date of randomization into the chemotherapy arms (i.e. after surgery for tumor resection), and not from the date of registration in the trial.

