12.0 COMPLIANCE AND DATA MANAGEMENT

12.1 Protocol Compliance:

The attending physician and oncology research nurse must see each patient after the first cycle, and subsequently after each 2 cycles of treatment prior to initiating the next cycle. All required interim and pretreatment data should be available and the physician must have made a designation as to tumor response and toxicity grade.

12.2 Data Entry:

All data will be entered on the computerized Protocol Data Management System (PDMS) of the Division of Medicine at MDACC. Patients must be registered in PDMS before a course of therapy can be given. A brief explanation for required but missing data should be recorded as a comment.

12.3 Accuracy of Data Collection:

A group consisting of the study chairman, the department chairman, the deputy chairman and an faculty member from the neuroradiology department will be the final arbiter of response or toxicity should a difference of opinion exist. The study chair will have the deciding vote in case of a tie.

Any life-threatening and/or unexpected and serious (grade 3 or 4) toxicity will be reported within 5 working days to the Study Chairman who, in turn, must notify the Surveillance Committee and the sponsoring agencies (See Appendix A).

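### Survival for surgical-arm patients should start at randomization, as their PFS does; counting from registration adds about 16 event-free days per patient

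*Combined protocol and SAP*

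**What the plan says.** Section 8.7 gives survival one definition for all patients: "From date of registration to date of death due to any cause". It makes no exception for the surgical arm.

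Section 8.6, immediately above, has a general rule for PFS, "From date of registration to the date of first observation of progressive disease", and then an exception: "Progression Free Survival (PFS) in patients enrolled in the surgical arm will be determined from the date of randomization". Section 5.2.2 states the same exception, and so does 11.2: "PFS in these patients will be determined from the date of randomization into the chemotherapy arms". All three say explicitly that the registration date is not to be used for these patients' PFS.

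The surgical pathway is in 5.2.2. "Ten patients who require resection for recurrent glioblastoma multiforme will be included in this arm of the study". Before the operation, "These patients will receive treatment with vorinostat at a dose of 400 mg once daily for 3 consecutive days prior to surgery". The third of these doses falls on the operation morning (also 7.9). Then: "Approximately 2 weeks after surgery is performed, each patient will be randomized to one of the three treatment arms". Section 12.2 places registration before any of this: "Patients must be registered in PDMS before a course of therapy can be given".

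Overall survival is a secondary endpoint in the three arms (1.2, item 2). Section 11.2 plans Kaplan-Meier estimates, log-rank tests and Cox models for it, and applies the intent-to-treat efficacy analysis to randomized and eligible patients.

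**The concern.** A surgical patient enters the survival comparison only by being randomized, and so must be alive at the end of the pre-operative dosing, the resection and the recovery period. Section 8.7 nevertheless starts the survival clock before all three. No death can occur in that interval among analysed patients, yet its length is added to each surgical patient's survival time. No delayed-entry adjustment is specified.

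The interval also says nothing about any of the three regimens. Every surgical patient has the same vorinostat lead-in and operation, including those later assigned to temozolomide plus isotretinoin, which contains no vorinostat.

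Two things are at stake: a slight overstatement of survival in arms that contain surgical patients, and a mismatch between endpoints. A surgical patient who dies without progression would have a survival time longer than the PFS time by the whole gap, although both end on the same day. The protocol rejects registration as the origin for these patients' PFS and gives no reason for keeping it for their survival.

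**Working it through.** The plan states no power, event count or effect size for survival, so there is no figure of its own to reproduce. The check compares the time origins and then sizes the gap.

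**Time origins**

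| Endpoint | Non-surgical patients | Surgical patients |
|---|---|---|
| PFS (8.6; surgical rule also in 5.2.2 and 11.2) | registration | randomization |
| Survival (8.7) | registration | registration |

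**Length of the gap**

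- Three daily doses, the third on the morning of surgery (5.2.2, 7.9): first dose to surgery = 3 − 1 = 2 days.
- Surgery to randomization (5.2.2): about 14 days.
- First dose to randomization: 2 + 14 = about 16 days; 16 / 30.44 = 0.53 month.

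The time from registration to first dose is not stated and would add to this. The two weeks are themselves approximate, so 16 days is an estimate and not a strict minimum.

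**Mean shift in survival** = (surgical patients × gap) / patients in the group

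- Whole trial, 10 of 135: 10 × 16 / 135 = 1.2 days. With an assumed gap of 24 days: 10 × 24 / 135 = 1.8 days.
- Four surgical patients in an arm of 21 (a tabled mean arm size of 20.8 appears in scenarios 2 and 5 at 3 patients per month): 4 × 16 / 21 = 3.0 days = 0.10 month.

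**Shift on the scale of the planned analysis.** Section 11.2 plans Kaplan-Meier, log-rank and Cox, so the median and an approximate hazard ratio are more relevant than the mean. Assume exponential survival with median M (not in the documents; taken as 5 to 12 months), rate λ = ln 2 / M, a fraction p of surgical patients in the arm, and gap g = 0.53 month. Solving (1 − p)·exp(−λt) + p·exp(−λ(t − g)) = 0.5 gives

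t = M + ln(1 − p + p·exp(λg)) / λ.

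For 3 surgical patients among 45 (p = 0.067), roughly an even split at full accrual, the median rises by about 1.1 days at every M in the range. The apparent hazard ratio, M / t, is 0.993 at M = 5 and 0.997 at M = 12. For all 10 among 45, an extreme split, the rise is about 3.6 days and the apparent ratio is 0.977 to 0.990.

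**How uneven the split could be.** With equal allocation to three arms, the chance that some arm receives 6 or more of the 10 surgical patients is about 23%. The chance that one arm receives all 10 is 3 × (1/3)^10, about 1 in 20,000.

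**The case against.** The case for leaving 8.7 alone has several sound parts.

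- **A single origin.** A reader might infer that the survival comparison mixes two time origins. It does not: 8.7 uses registration for everyone, and it is PFS that has two nominal origins. The amendment would give survival the same nominal pair as PFS. This stands. The complaint is only that, for surgical patients, registration lies more than two weeks before any arm is assigned. The documents do not say whether registration and randomization fall on the same day for non-surgical patients.
- **No systematic bias between arms.** A reader might infer the usual immortal-time bias, in which surviving determines the group a patient joins. The documents do not support that. The interval ends before randomization and is the same whichever arm follows, so it favours an arm only if surgical patients happen to be unevenly allocated, and any arm could gain.
- **Never-randomized patients.** A reader might infer that a patient who registers and dies before randomization has a survival time but no arm. Section 11.2 already places such a patient outside the efficacy set. That exclusion settles who is analysed, but it is also what makes the interval event-free for those who remain.
- **Larger figures.** All 10 surgical patients in an arm of 14 would give 10 × 16 / 14 = 11.4 days, or 0.38 month. That split is close to impossible under equal allocation. The smallest tabled arms are also those assigned less often or dropped, so the figure should not be used as a realistic bound.
- **Registration as a legitimate choice.** Counting survival from trial entry is recognised practice, and nothing requires survival and PFS to share an origin. This is fair in general. It is weaker here because the protocol explicitly rejects that origin for the same patients' PFS, three times, and explains no difference.

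**Conclusion.** The point holds as a minor inconsistency in the definition of a secondary endpoint. For up to 10 surgical patients, survival as defined includes about 16 days that precede arm assignment and are event-free because only randomized patients are analysed. Across the trial that is about 1.2 days on average; for a typical split it moves an arm's median by about one day. Arm selection, early stopping, arm dropping and sample size all rest on PFS and are unaffected.

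The size rests on the two-week interval being met, on registration at about the time of the first pre-operative dose, and, for the median and hazard-ratio figures only, on exponential survival with an assumed median of 5 to 12 months. A longer wait between registration and first dose would increase the shift in proportion.

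**What to change.** Add one sentence to 8.7: for patients in the surgical arm, survival is measured from the date of randomization, as for PFS in 8.6. Repeat it in 11.2 beside the existing PFS sentence, so that the statistical section carries both rules.

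Optionally, report deaths and withdrawals between registration and randomization in the surgical arm separately, since they fall outside the efficacy set and would otherwise not be visible.

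The cost is a sentence or two of text. Both dates are already needed for the existing definitions; treatment, sample size, data collection and the adaptive algorithm do not change.

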9.0 DATA AND SAFETY MONITORING

9.1 Safety Assessments and Toxicity Monitoring:

All patients receiving Vorinostat, Isotretinoin and Temozolomide will be evaluated for safety. The safety parameters include all laboratory tests and hematological abnormalities, CNS observations, physical examination findings, and spontaneous reports of adverse events reported to the investigator by patients. All toxicities encountered during the study will be evaluated according to the NCI Common Terminology Criteria (CTCAE) version 3.0 and recorded prior to each course of therapy. Life-threatening toxicities should be reported immediately to the Study Chair, Institutional Review Board (IRB), and the FDA.

To provide formal safety monitoring in the Phase II portion of the trial, after enrollment of every 10 patients into each of the three arms, we will assess the group for toxicity. If dose limiting toxicity as defined in the phase I portion of the trial is reached =/> 1/3 of patients despite dose reduction, the arm will stop accrual. If dose reduction permits continuation of treatment in these patients, the

starting dose levels for the remainder of the patients on the trial will be modified to a lower starting dose (-1) level specified in the dose modification section

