5.3. Definition of dose limiting toxicities (DLT)

Toxicities will be graded according to the Common Terminology Criteria for Adverse events (CTCAE) Version 3.0. (see Appendix B). If multiple toxicities are seen, the presence of DLT should be based on the most severe toxicity experienced. DLT will be defined as any of the following events occurring during treatment and attributable to the study drugs:

5.3.1 Any grade 4 hematological toxicity excluding lymphopenia . (if the toxicity is Grade 4 neutropenia without fever, it must NOT resolve/regress to \leq Grade 1 within 7 days of onset to be considered a DLT).

5.3.2 Any non-hematologic grade 3 toxicity, weight gain (in patients on steroids), alopecia, and venous thromboembolic disease *. Grade 3 nausea, vomiting, or diarrhea that cannot be controlled by medical therapy will be considered dose-limiting. Isolated laboratory abnormalities not of clinical significance will be discussed with the IRB and the decision to declare these DLTs will be based on the IRB recommendations.

5.3.3 Failure to recover from toxicities to be eligible for re-treatment within 4 weeks of the last dose of the drugs.

*Non-Relevant Toxicities for Brain Tumor Protocols

Lymphopenia is a common finding among patients with primary brain tumors and is directly attributable to concurrent use of corticosteroids. To date, even Grade III lymphopenia has not been associated with a worsening of clinical outcome. Therefore, we will not consider this parameter in the determination of optimal dosing of drugs.

Weight gain is a common finding among patients with primary brain tumors. This too is directly attributed to the concurrent use of corticosteroids. Doses of steroids or study agents will not be modified as a consequence of weight gain. Corticosteroid dosage will be based on maintenance of control of edema in the brain and the standard clinical practice to use the minimal effective dose of corticosteroids will be employed.

Alopecia is a common occurrence in patients with brain tumors as a consequence of cranial radiotherapy. Alopecia will not be recorded or graded as toxicity.

Venous thromboembolic disease is a common complication occurring in up to 30% of patients with malignant gliomas [32, 33]. In this study, patients who develop deep vein thrombosis may receive anticoagulation and resume therapy once they are stable on anticoagulation. Grade III deep vein thrombosis will not be considered a DLT.

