5.4. Dose modifications

5.4.1 Subsequent Cycles

Treatment cycles will be repeated every 28 days (+ 2 days) from day 1 provided that the tumor has not progressed and the patient has recovered from treatment-related adverse events associated with a prior course. Recovery has occurred once all of the following conditions have been met:

a) ANC >1500/mL;

b) Platelet Count >100,000/mL;

c) All drug-associated non-hematological toxicities have recovered to either Grade 0 or 1(except for deep venous thrombosis as below).

If recovery has not occurred by **Day 28** (+ 3 days), the subsequent cycle will be delayed until these criteria have been met. If the patient has not recovered within 4 weeks of rest, he/she will be taken off study. However, if the patient develops a lower extremity deep venous thrombosis and requires anticoagulation or intervention (grade 3 toxicity), treatment may be restarted after a 2 week rest period if the patient

is stably anticoagulated and is judged medically stable to begin chemotherapy, in the opinion of the treating physician. (Please note: DVT is graded in the CTC version 3.0 as grade 1= not defined, grade 2= DVT without need for anticoagulation or intervention, grade 3= DVT needing anticoagulation or intervention).

The administration of vorinostat, isotretinoin and temozolomide in subsequent cycles will continue at the same doses without interruption as long as there is no tumor recurrence or progression and toxicity is acceptable.

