Dose reductions: If any treatment related non-hematologic AE observed was grade > 2 (except alopecia, lymphopenia, nausea, vomiting, weight gain and DVT/PE) and/or if platelets < 50×10^{9} /L and/or ANC < 1×10^{9} /L, then the dose should be reduced by one dose level. Patients who require more than three dose reductions will have treatment stopped.

If any treatment-related non-hematologic AE observed was grade 4 (except alopecia, lymphopenia, nausea, vomiting, weight gain and DVT/PE) then temozolomide treatment should be stopped.

Subsequent cycles: Any dose reductions of temozolomide will be determined according to: (1) non-hematologic AE during the preceding

treatment cycle, as well as (2) the lowest ANC and platelets observed. No dose escalation should be attempted. The same dose reductions as for the second cycle should be applied. Important: If the dose was reduced or delayed for AEs, there will be no dose re-escalation in subsequent treatment cycles.

Summary of Dose Modifications or Discontinuation for Temozolomide-Related Adverse Events

Worst Treatment-Related Non-Hematologic AE (except for alopecia, nausea, and vomiting) During the Previous Cycles			
Grade	Dose Modification		
0-2	No dose modifications for non-hematologic AEs. Dose reductions based on ANC and platelet counts are applicable.		
3	Reduce by one dose level (except alopecia, lymphopenia, nausea, vomiting, weight gain and DVT/PE).		
4	Stop (except alopecia, lymphopenia, nausea, vomiting, weight gain and DVT/PE). Dose modifications based on ANC and platelet counts are not applicable.		

Worst Treatment-Related Hematologic AE During the Previous Cycle

Worst A	ΑE	Platelets		
		≥100 x 10 ⁹ /L	50 – 99 x 10 ⁹ /L	< 50 x 10 ⁹ /L
	≥ 1.5 x 10 ⁹ /L	Dose unchanged	Dose unchanged	Reduce by 1 dose level
ANC	≥1 & <1.5 x 10 ⁹ /L	Dose unchanged	Dose unchanged	Reduce by 1 dose level
	< 1 x 10 ⁹ /L	Reduce by 1 dose level	Reduce by 1 dose level	Reduce by 1 dose level

Note: A complete blood count must be performed on days 14 and 28 (\pm 72 hours) after the first daily dose of each treatment cycle.

Hematologic AE on Day 1 of Each Cycle (within the prior 72 hours before Day 1)			
AE	Delay		
ANC< 1.5 x 10 ⁹ /L and/or Platelet count < 100 x 10 ⁹ /L	Delay up to 4 weeks until all resolved. If unresolved after 4 weeks then stop. If resolved, dose delay/reductions based on non-hematologic AEs are applicable. If treatment has to be delayed for AEs, then no escalation is possible.		

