T+A	4	0.003	0.003	0.803	23.7 (10,64)
V+A+T	7	0.949	0.727	0.003	53.2 (11,98)

Scenario 6

Average Trial Length 6.28 months

Arm	True Median Survival	Pr(Selected)	Pr(Selected Early)	Pr(Stopped Early)	# Patients (2.5%,97.5%)
V+A	1	0.02	0	0.768	10.4 (10,14)
T+A	1	0.022	0	0.762	10.5 (10,14)
V+A+T	1	0.024	0	0.757	10.5 (10, 15)

(Abbreviations: PFS: Progression free survival; V, vorinostat; A, accutane (isotretinoin); T, temozolomide)

Patients' demographic information at baseline will be analyzed, with data summarized in tables listing the number of subjects per treatment group in order to assess comparability. The Student t-test or the Wilcoxon rank sum test will be used to compare continuous variables between two different patient groups. The chi-squared test or the Fisher exact test will be applied to assess the association between two categorical variables.

Time-to-event outcomes, including progression-free survival and overall survival, will be estimated using Kaplan-Meier method. The log-rank test will be performed to test the difference in time-to-event distributions between patient groups. Cox proportional hazards model will be utilized to include multiple covariates in the time-to-event analysis.

Toxicity data will be summarized by frequency tables. The association between the types and severity of toxicity and the treatment groups will be evaluated. No formal statistical testing will be performed on these summary data.

To provide formal safety monitoring in the Phase II portion of the trial, after enrollment of every 10 patients into each of the three arms, we will assess the group for toxicity. If dose limiting toxicity as defined in the phase I portion of the trial is reached =/> 1/3 of patients despite dose reduction, the arm will stop accrual. If dose reduction permits continuation of treatment in these patients, the starting dose levels for the remainder of the patients on the trial will be modified to a lower starting dose (-1) level specified in the dose modification section.

For the efficacy endpoint, intent-to-treat analysis will be applied to the randomized and eligible patients. For the toxicity endpoint, as-treated analysis

will be used to include any patient who received the treatment – regardless of the eligibility nor the duration or dose of the treatment received.

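### The Phase II toxicity stopping rule does not say whether a DLT that precludes any dose reduction counts towards closing an arm, and its looks are tied to enrolment with no observation window

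*Combined protocol and SAP*

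**What the plan says.** Section 9.1, repeated in 11.2, schedules the review: "after enrollment of every 10 patients into each of the three arms, we will assess the group for toxicity". Two branches follow.

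- Closing branch: if DLT, as defined for Phase I, is "reached =/> 1/3 of patients despite dose reduction, the arm will stop accrual".
- Lower-dose branch: "If dose reduction permits continuation of treatment in these patients, the starting dose levels for the remainder of the patients on the trial" move to the -1 level.

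Other sections determine who can reach a reduced dose.

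- Section 5.3.3 makes failure to recover in time for re-treatment within 4 weeks a DLT in its own right. Section 5.4.1 then says: "If the patient has not recovered within 4 weeks of rest, he/she will be taken off study".
- Section 5.4.2.3 says that after a treatment-related grade 4 non-hematologic event (with listed exceptions) "then temozolomide treatment should be stopped". There is no reduction step.
- Most other severe events lead to a reduction: low ANC or platelets on temozolomide (5.4.2.3), and grade 3 or greater toxicity on vorinostat (5.4.2.1) or isotretinoin (5.4.2.2).

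The Phase I rules in 5.1.3 count patients with a DLT, with no condition about dose reduction. The documents give no operating characteristics for the Phase II toxicity rule.

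**The concern.** The closing branch is worded as if every patient with a DLT goes on to a reduced dose, and the other branch as if reduction allowed treatment to go on. A patient who never receives a reduced dose fits neither. These are among the most serious outcomes, so a literal count could leave out the events that a safety rule most needs to see. Two people applying the rule to the same data could reach opposite decisions.

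This matters because the randomization adapts to PFS alone. A non-fatal DLT that ends treatment is not a PFS event, so the algorithm can keep favouring an arm with many of them. In the plan's simulations (scenarios 2 to 5, both accrual rates) the best arm receives on average 36 to 61 patients, with upper limits of 90 to 101. Arm 2 has no Phase I cohort in this trial (5.1.2).

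Timing is a second gap. A look is due at each tenth enrolment in an arm, and no minimum follow-up is stated. Recently enrolled patients can enter the denominator before they have had time to show a DLT.

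**Working it through.** **Which patients fall between the branches.**

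| First DLT | What the plan prescribes | Reduced dose reached? | Arms |
|---|---|---|---|
| No recovery within 4 weeks (5.3.3) | Off study (5.4.1) | No | 1, 2, 3 |
| Fatal toxicity | – | No | 1, 2, 3 |
| Temozolomide-related grade 4 non-hematologic | Temozolomide stopped (5.4.2.3) | Not for temozolomide | 2, 3 |
| "Any grade 4 hematological toxicity excluding lymphopenia", ANC or platelets on temozolomide | Reduce one level (5.4.2.3) | Yes | 2, 3 |
| Grade 3 or greater on vorinostat or isotretinoin, recovered | One level lower (5.4.2.1, 5.4.2.2) | Yes | per drug |

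The first row is the clearest: it is a DLT by the plan's own definition and removes the patient. Rows two and three rest on an implied point, because 5.3.2 names only grade 3 for non-hematologic toxicity and does not mention grades 4 and 5.

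**Effect of the reading.** The plan states no figure to reproduce. One third of 10, 20, 30 and 40 patients, rounded up, gives boundaries of 4, 7, 10 and 14. Three inputs are assumptions, not taken from the documents: p, the share of patients with a first DLT; f, the share of first DLTs that preclude reduction; q, the chance of another DLT after reduction.

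- Literal count: p(1 − f)q
- Treatment-ending DLTs also counted: p[f + (1 − f)q]

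With p = 0.50, f = 0.5, q = 0.4:

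- Literal: 0.5 × 0.5 × 0.4 = 0.10, and P(X ≥ 4 | n = 10) = 0.013.
- Treatment-ending counted: 0.5 × (0.5 + 0.5 × 0.4) = 0.35, and P(X ≥ 4 | n = 10) = 0.49.

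Range, as the probability of closing at 10 patients / by 40 patients over four cumulative looks (exact binomial recursion):

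| p | f | q | Literal | Treatment-ending counted |
|---|---|---|---|---|
| 0.30 | 0.5 | 0.5 | 0.5% / 0.5% | 16.9% / 25.8% |
| 0.40 | 0.5 | 0.5 | 1.3% / 1.4% | 35.0% / 57.9% |
| 0.50 | 0.25 | 0.5 | 10.0% / 13.9% | 38.4% / 63.3% |
| 0.50 | 0.5 | 0.25 | 0.2% / 0.2% | 38.4% / 63.3% |
| 0.50 | 0.5 | 0.5 | 2.8% / 3.2% | 55.3% / 85.1% |
| 0.50 | 0.5 | 1 | 22.4% / 35.8% | 82.8% / 99.3% |
| 0.50 | 1 | any | 0 / 0 | 82.8% / 99.3% |

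If f = 0 the two readings coincide. If f = 1 the literal rule never closes an arm, whatever p is.

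**Follow-up at a look.** Patients with under 28 days = monthly accrual to the arm × 28/30.4. The 28-day window is one cycle; the plan sets none. With the minimum randomization probability of 0.1 and all three arms open, the largest allocation to one arm is 1 − 2 × 0.1 = 0.8.

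- 5 per month, equal allocation: 5/3 = 1.67 per arm; 1.67 × 28/30.4 = 1.5 of 10.
- 5 per month, 80% allocation: 4 × 28/30.4 = 3.7 of 10. This is possible only after the first 30 patients, who are randomized equally.
- 3 per month: 1 × 28/30.4 = 0.9 and 2.4 × 28/30.4 = 2.2 of 10.

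**The case against.** The two sentences can be read as a pair. The second covers patients whom reduction keeps on treatment, so the first would cover those it does not, and treatment-ending DLTs would count. This is a fair reading and may be the intended one. A reader might infer from the literal wording that such DLTs can never close an arm; the documents do not establish that. What stands is that they do not say which reading applies.

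A reader might also infer that grade 4 events in general drop out. They do not: most lead to a reduction and stay within the rule. In Arm 1, which has no temozolomide, the gap is limited to fatal toxicity and non-recovery. In Arms 2 and 3 the grade 4 rule stops temozolomide only.

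Other controls exist. Death is a PFS event (8.6) and feeds the rule that drops an arm when the probability of a median PFS above 3 months is below 0.01 (11.2). Life-threatening toxicity goes at once to the IRB and FDA (9.1), a DSMB was notified of the carboplatin results (2.11), and Arm 2's regimen rests on a cited phase I study (5.1.2). These reduce the severity, but none is a numerical Phase II toxicity threshold.

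It would be tempting to compare 0.013 with 0.83, the probability of closing at 10 patients if every DLT counts at p = 0.50. That comparison mixes two effects, because it also counts DLTs that reduction managed, for which the plan has its own response. Counting every DLT against the same 1/3 would collapse the two branches: at true DLT rates of 20% and 30%, both below the threshold, it would close an arm by 40 patients with probability 17% and 58%.

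Finally, a look due after enrolment need not happen on the day of enrolment. That is true, but no window is stated.

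**Conclusion.** The concern holds as an undefined numerator and an unspecified observation window, not as a proven exclusion of severe events. The non-recovery DLT shows the gap most clearly and needs no inference about grading. The reading decides whether the rule can act: 0.013 against 0.49 at the first look under the stated assumptions, and zero on the literal count if every first DLT ends treatment. Those sizes depend on p, f and q, which are illustrative; the difference shrinks as f falls and vanishes at f = 0. The dilution of 1.5 to 3.7 patients in 10 depends on accrual of 5 per month, the allocation, a 28-day window and a look made at enrolment. This should be fixed before the rule is applied, but the other safety controls and the available benign reading keep it from being a fatal flaw.

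**What to change.** In 9.1 and 11.2, in identical words:

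- State that the closing-branch numerator includes patients whose DLT precluded dose reduction (death, permanent discontinuation or removal from study) as well as those with a DLT after reduction.
- Define the denominator as patients in that arm who have completed a stated observation window, for example cycle 1, or have had a DLT.
- Run the looks separately and cumulatively for each arm, at each 10 such patients, so that a DLT after reduction that falls beyond the window enters at a later look.
- Keep the two branches and the 1/3 threshold.
- Report the rule's operating characteristics over a range of DLT rates and treatment-ending shares.

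The sponsor should reconcile 5.3 (including whether grade 4 and 5 non-hematologic events are DLTs), 5.4, 9.1 and 11.2. How individual patients are managed after a toxicity is for the sponsor to settle; no clinical rule is proposed here.

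The cost is a rewording in two places and a short calculation, using toxicity data already collected. Each look would come about one cycle later than at enrolment, and an arm may close earlier than under the literal count.
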